4. SUBJECT SELECTION CRITERIA

The Investigator should keep a record, the patient screening log, of patients who entered prestudy screening.

Each patient should meet all of the inclusion criteria and none of the exclusion criteria for this study. Under no circumstances can there be exceptions to this rule.

4.1 Inclusion criteria

For inclusion in the study, patients should fulfil the following criteria:

1. Provision of signed and dated, informed consent prior to any study specific procedures

2. Female patients between the ages of 18 to 45 years (inclusive) with suitable veins for cannulation or repeated venipuncture
3. A diagnosis of polycystic ovary disease; patient must fulfil all of the following criteria:
 - Polycystic ovaries (previously documented ultrasound from records are acceptable)
 - Free testosterone at screening greater than 85% of the age-specific upper limit of normal (ULN) as specified in [Appendix I](#)
 - Total testosterone < 5 nmol/L at screening
4. Amenorrhea or oligomenorrhea (defined as ≤ 6 menses per year)
5. Body mass index (BMI) between 18 and 40 kg/m² (inclusive)
6. Females must have a negative serum pregnancy test at screening and a negative urine pregnancy test before randomisation, must not be breast-feeding, must not have been pregnant within the 6 months prior to screening, and must not expect to conceive within the projected duration of the study
7. Patient is permanently or surgically sterilised or practices abstinence as a lifestyle choice, or who agrees to use/have their partner use effective methods of birth control for the duration of their study participation

Permanent sterilisation includes bilateral salpingectomy but excludes bilateral tubal occlusion. Effective methods of birth control within the study treatment period are defined as partner use of male condom plus one of the following: spermicide, vasectomy, tubal occlusion, or an intrauterine device that does not contain steroid hormones.

For inclusion in the optional genetic component of the study:

8. Provision of signed, written, and dated informed consent for optional genetic research. If a patient declines to participate in the genetic component of the study, the patient will not be excluded from the other aspects of the study.

4.2 Exclusion criteria

Patients should not enter the study if any of the following exclusion criteria are fulfilled:

1. Is perimenopausal or has reached natural menopause, defined as FSH > 10 IU/L
2. Has menstruated within the month prior to the baseline visit

3. Clinically relevant disease and abnormalities (past or present), and in particular causes of abnormal vaginal bleeding, which, in the opinion of the Investigator, may either put the patient at risk to participate in this study or may influence the results of the study or the patient's ability to participate in the study
4. Significant illness, as judged by the Investigator, within 2 weeks of Day -1
5. Patient has clinical, laboratory, or ECG evidence of uncontrolled hypertension (defined as systolic blood pressure of ≥ 160 mmHg and/or diastolic blood pressure of ≥ 100 mmHg); uncontrolled diabetes; or significant pulmonary, renal, hepatic, endocrine, or other systemic disease in the opinion of the Investigator
6. Patients who have had a hysterectomy or bilateral oophorectomy or both; if the patient has had prior ovarian cystectomy(ies), unilateral oophorectomy, uterine surgery such as myomectomy(ies) or polypectomy(ies), etc., then these patients may be considered on a case-by-case basis by the AstraZeneca Medical team, with the aim to exclude anyone who no longer has ovarian function or a functional endometrium
7. Patient has a history of Gilbert's syndrome, infectious hepatitis, or other significant hepatic disease (eg, chronic hepatitis, cirrhosis, autoimmune hepatitis, primary sclerosing cholangitis, nonalcoholic steatohepatitis, or hereditary liver disease) in the opinion of the Investigator
8. Patient has a history of gastric or small intestinal surgery (including gastric bypass surgery or banding), or has a disease that causes malabsorption
9. Patient has a history of hypothyroidism or evidence of hypothyroidism from the screening thyroid tests, as judged by the Investigator
10. Clinically significant abnormal ECG and/or abnormalities in ECG at screening as judged by the Investigator
11. A marked prolongation of QT/QTc interval (eg, repeated demonstration of a QTc interval > 450 ms)
12. A history of additional risk factors for Torsades de Pointes (eg, heart failure, hypokalemia, or family history of long QT syndrome)
13. The use of concomitant medications that prolong the QT/QTc interval
14. Positive human immunodeficiency virus (HIV), hepatitis B, or hepatitis C serology evaluations at the screening visit
15. Patient has a history of hypersensitivity to more than 2 chemical classes of drugs, including prescription and over-the-counter medications

16. Past (within 1 year of enrolment) or present alcohol or substance abuse or a positive test for alcohol or drugs of abuse at screening or is a “recreational user” of illicit drugs or prescription medications
17. Patient consumes 3 or more alcoholic drinks per day (Note: 1 drink = 12 oz [360 mL] can/bottle of beer, 4 oz [120 mL] of wine, or 1 oz [30 mL] of liquor)
18. Has received another new chemical entity (defined as a compound which has not been approved for marketing) or has participated in any other clinical study that included drug treatment within at least 3 months of the first administration of IP in this study. The period of exclusion begins 3 months after the final dose or 1 month after the last visit, whichever is the longest. (Note: patients consented and screened, but not randomised in this study or a previous study are not excluded.)
19. Blood loss in excess of 200 mL within 30 days of Day -1, in excess of 500 mL within 56 days of Day -1, in excess of 1350 mL within 1 year of Day -1, or donation of blood products within 14 days of Day -1
20. Patient has a history of neoplastic disease within 5 years prior to signing informed consent, except for adequately treated basal cell, squamous cell skin cancer, or in situ cervical cancer
21. Involvement in the planning and/or conduct of the study (applies to any AstraZeneca employee and their close relatives and/or staff at the study site, regardless of their role in accordance with their internal procedures) or
22. Previous randomisation to treatment in the present study
23. Inability to understand or cooperate with the requirements of the study
24. Patient is legally or mentally incapacitated
25. Patient has abnormal screening laboratory values as per the guidelines listed below or other clinically significant, unexplained laboratory abnormality according to the Investigator:
 - Aspartate aminotransferase (AST) >1.5 times ULN
 - Alanine aminotransferase (ALT) > 1.5 times ULN
 - Total bilirubin >1.5 times ULN
 - Serum creatinine >2.0 times ULN
 - Hematocrit less than the lower limit of normal
 - Prolactin >2.0 times the ULN

26. Patients who are withdrawing from oral contraceptives if their LH levels are below 3 IU/L when retested within 21 to 2 days of the baseline visit
27. Patient has taken any potent or moderate CYP3A4 or CYP2C9 inhibitors, potent or moderate CYP3A4 or CYP2C9 inducers, hormonal contraceptives, antiandrogenic drugs, or other medications for the time frame specified in [Table 3](#)
28. Patient reporting suicidal ideation of Type 4 or 5 in the past 2 months or suicidal behaviour in the past 6 months as measured by the C-SSRS at baseline

In addition, the following are considered criteria for the exclusion from the optional genetic component of the study:

29. Previous bone marrow transplant
30. Non-leukocyte depleted whole blood transfusion within 120 days of the date of the genetic sample collection

Procedures for withdrawal of incorrectly enrolled patients are discussed in [Section 5.3](#).

5. STUDY CONDUCT

5.1 Restrictions during the study

Patients will be required to:

1. Patients are to fast from 2 hours prior to the morning dose until 1 hour after dosing on Days 7 and 28.
2. Patients will be provided with a dosing diary to record the time they take their medication each day and symptom diary paper questionnaires to be completed every evening before bedtime.
3. Patients are to abstain from taking any medication (prescribed or over the counter products) except acetaminophen (up to 4 gram per day) or topical preparations, as specified in [Section 5.6](#), until completion of the follow-up visit.
4. Patients are to abstain from blood or plasma donation until 3 months after completion of the follow-up visit.
5. Patients are not to consume more than 3 alcoholic drinks per day from screening until completion of the final study visit.
6. Patients who are not permanently or surgically sterile must use effective non-hormonal methods of birth control, such as strict abstinence or use/have their partner use effective non-hormonal methods of birth control for the duration of their

study participation. Acceptable barrier methods of contraception include condom or occlusive cap (diaphragm or cervical/vault caps) with spermicidal foam/gel/film/cream/suppository.

7. Any intake of grapefruit, Seville oranges, or products containing grapefruit or Seville oranges, within 7 days of the first administration of IP and through duration of IP administration is not permitted.
8. Patients should not increase level of strenuous exercise or increase caffeine intake during participation in the study.

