On Days -1, 7, and 28, multiple samples for the analyses of LH, FSH, and testosterone profiles will be collected prior to dosing until 8 hours following the morning dose. On Day -1, sampling will begin just prior to the anticipated time of dosing on subsequent study days and continue for 8 hours. Intensive sampling should begin by 9 AM on Day -1 and will be initiated at approximately the same time on each subsequent visit (± 1 hour). Patients will be asked to complete the HRQoL short form 36 (SF-36; see [Appendix E](#)) at baseline (Day -1) and on Day 28. A site symptoms questionnaire will be completed at each study visit from Day -1 through Day 28 (see [Appendix F](#)). A symptoms diary questionnaire will be completed at the patients' homes each evening from Day -1 through Day 28. Serial PK samples will be collected prior to dosing until 8 hours following the morning dose on Days 7 and 28. On Days 14 and 21, patients will report to the clinic to undergo safety assessments.

Safety evaluations will include assessment of AEs, use of concomitant medications, clinical laboratory tests, measurement of vital signs, 12-lead electrocardiograms (ECGs), physical examinations, and Columbia-Suicide Severity Rating Scale (C-SSRS) assessments.

A study flow chart is presented in [Figure 1](#), a schedule of all assessments is presented in [Table 1](#), and the details of blood sample collection are presented in [Table 2](#).

Figure 1 Study flow chart

Outpatient administration of IP begins the morning of Day 1 for all treatments. A window of ± 1 day is allowed for the Day 7, 14, 21, and 28 visits.

^a There will be 56 patients (14 per each treatment group) enrolled to have approximately 12 evaluable patients in each treatment group.

^b Applies only to patients who require washout of oral contraceptives or have a screening visit more than 3 weeks prior to the baseline visit.

Table 1 Study plan

	Screening ^a		Baseline					Follow-up	Early discontinuation
	Visit number	1	2	3	4	5	6	7	8
	Study day relative to first dose	-60 to -2	-21 to -2	-1	+7±1	+14±1	+21±1	+28±1	+42±3
Informed consent	X								
Review of inclusion/exclusion criteria	X	X							
Demography	X								
Medical/surgical history	X								
Ultrasound	X ^b								
Serology assessment ^c	X								
Test for alcohol and drugs of abuse ^d	X		X						
Pregnancy test	X ^e	X	X	X	X	X	X	X	X
Randomisation			X						
Dispense IP ^f			X						
Dispense dosing diary ^g			X						

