Fast for 2 hours prior to and 1 hour following morning dose				X			X		
Administer morning dose in clinic				X	X ^h	X ^h	X ⁱ		
Assessment of compliance				X	X	X	X		
Return of unused IP ^f				X	X	X	X		
Record concomitant medications ^j	X	X	X	X	X	X	X	X	X
Record AEs ^k	X	X	X	X	X	X	X	X	X
Physical examination ^l	X		X				X	X	X

Table 1 Study plan

	Screening ^a		Baseline					Follow-up	Early discontinuation
	Visit number	1	2	3	4	5	6	7	8
	Study day relative to first dose	-60 to -2	-21 to -2	-1	+7±1	+14±1	+21±1	+28±1	+42±3
Weight	X		X	X			X	X	X
Height and BMI	X								
Vital signs ^m	X		X	X			X	X	X
12-lead ECG	X		X	X ⁿ			X ⁿ	X	X
Haematology ^o	X	X	X	X	X	X	X	X	X
Clinical chemistry	X	X	X	X	X	X	X	X	X
Urinalysis	X	X					X	X	X
C-SSRS ^p			X	X	X	X	X	X	X
Pharmacokinetic samples ^q				X			X		X
HRQoL - SF-36			X				X		X
Symptoms site questionnaire			X	X	X	X	X		X
Symptoms diary questionnaire ^r			X	X	X	X	X		
High frequency LH samples ^s			X	X			X		
Well-defined FSH ^t			X	X			X		
Single sample LH	X	X						X	X
Single sample FSH	X							X	X
Single sample testosterone (total/free)	X	X						X	X
Well-defined testosterone (total/free) ^t			X	X			X		
4-β-OH cholesterol			X				X ^u		

Table 1 Study plan

	Screening ^a		Baseline					Follow-up	Early discontinuation
Visit number	1	2	3	4	5	6	7	8	
Study day relative to first dose	-60 to -2	-21 to -2	-1	+7±1	+14±1	+21±1	+28±1	+42±3	
6-β-OH testosterone			X				X ^u		
TSH and T4 (total and free) ^v	X		X	X			X	X	
HbA _{1c} ^v			X				X	X	
IGF-1, progesterone, E2 ^v			X	X			X	X	
Prolactin ^v	X		X	X			X	X	
Consent and blood sample for genetic analysis (optional) ^w				X					

BMI body mass index; HIV human immunodeficiency virus; OH hydroxy; SAE serious AE.

^a Patients who must discontinue the use of oral contraceptives prior to the study will return to the clinic on Days -21 to -2 for repeat laboratory assessments. Patients who do not require a washout of oral contraceptives, but screening assessments were performed more than 3 weeks from the baseline visit, will also return to the clinic on Days -21 to -2 for repeat laboratory assessments.

^b May be performed if there is no previously-documented ultrasound for diagnosis of PCOS.

^c Screen for HIV, hepatitis B, and hepatitis C.

^d Random drug and alcohol screening at subsequent visits may be performed at the discretion of the Investigator. See Section 6.3.5 for a list of analytes.

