5.5.2 Doses and treatment regimens

At Visit 2, eligible patients will be randomly assigned to 1 of 4 treatment groups as below.

The IP will be administered as two AZD4901 and/or placebo tablets twice daily from Day 1 through the morning dose on Day 28, as follows:

- 20 mg AZD4901 once daily: one 20-mg AZD4901 tablet and 1 placebo tablet for the morning dose and 2 placebo tablets for the evening dose
- 20 mg AZD4901 twice daily: one 20-mg AZD4901 tablet and 1 placebo tablet for both the morning and evening doses
- 40 mg AZD4901 twice daily: two 20-mg AZD4901 tablets for both the morning and evening doses
- Placebo: two matching placebo tablets for both the morning and evening doses

Patients will be required to fast from 2 hours prior to the morning dose until 1 hour postdose on Days 7 and 28.

On Days 7 and 28, the morning dose of IP will be administered in the clinic with 240 mL water. On Days 14 and 21, it is suggested patients take their morning dose of IP with sufficient water in the clinic; however, if this is not practical, dosing may occur at home with the patient reporting to the clinic later in the day for scheduled procedures. Otherwise, all doses are taken with sufficient water on an outpatient basis and recording of dates and times in the dosing diary. At each study visit, patients are to bring diaries and unused IP supplies for assessment of treatment compliance. At the last study visit, patients are to return any unused IP supplies.

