11.4 Calculation or derivation of pharmacodynamic variable(s)

The PD analyses will be performed at _____ with select analyses performed by AstraZeneca or designee. _____ SOPs and Work Instructions will be used for analyses performed by _____ as the default methodology if not otherwise specified.

Change-from-baseline (Day-1) for LH, FSH, free and total testosterone concentrations, and the components of the monitoring sample (estradiol [E2], progesterone, prolactin, TSH, T4 [total and free], HbA_{1c}, and IGF-1), as appropriate, will be calculated as:

- Absolute change: $X_t - X_0$
- Percent change from baseline: $100 \times (X_t - X_0) / X_0$
- Ln-ratio: $\ln(X_t / X_0)$

where X_t is a patient's measured value at time t and X_0 is the time matched measurement at baseline for LH, FSH and free and total testosterone and a single value baseline for other analytes listed above.

Primary

- LH AUC₍₀₋₈₎ on Day 7: Area under the plasma concentration-time curve from time zero to 8 hours calculated by linear up/log down trapezoidal summation on observed concentrations

Secondary

- Change-from-baseline (Day-1) for free and total testosterone concentrations on Days 7 and 28
- AUC₍₀₋₈₎ for LH on Day 28 on observed concentrations

Where possible, the following PD parameters will be determined for observed concentrations of LH, testosterone, and FSH samples collected on Days -1, 7, and 28:

- AUC₍₀₋₈₎ for LH
- Free and total testosterone AUC₍₀₋₈₎, calculated by linear up/log down trapezoidal summation
- FSH AUC₍₀₋₈₎, calculated by linear up/log down trapezoidal summation
- An evaluation of LH pulse interval and amplitude ([Johnson 2008](#)) (to be performed by AstraZeneca)

- Free and total testosterone C_{\max} : Maximum observed plasma concentration, obtained directly from the observed concentration versus time data
- Free and total testosterone C_{\min} : Minimum observed plasma concentration, obtained directly from the observed concentration versus time data
- FSH C_{\max} , obtained directly from the observed concentration versus time data.
- FSH C_{\min} , obtained directly from the observed concentration versus time data.

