12.2.6 Pharmacodynamics

Observed PD concentrations (including those of the monitoring samples) and their corresponding change-from-baseline values will be listed for individual patients and summarised with appropriate descriptive statistics across all treatments and sample collection points. Descriptive statistics will be provided for absolute change, percent change from baseline, and ln-ratio to baseline values (as defined in Section 11.4). Descriptive statistics for the ln-ratio to baseline will be exponentiated for display in linear scale.

Pharmacodynamic parameter ($AUC_{(0-8)}$, C_{\max} , C_{\min}) values for individual patients will be listed for LH, free testosterone, total testosterone and FSH.

Descriptive statistics (n, mean, geometric mean, SD, and CV) will be calculated for the PD parameters ($AUC_{(0-8)}$ for LH and $AUC_{(0-8)}$, C_{\max} , and C_{\min} for free and total testosterone and FSH, including ratio to baseline in $AUC_{(0-8)}$, C_{\max} , and C_{\min}).

Comparisons of $AUC_{(0-8)}$ for LH, total testosterone, free testosterone, and FSH will be conducted using an analysis of variance (ANOVA) model on the ln-transformed ratio to baseline values ($\ln[AUC_{(0-8)}/AUC_{(0-8)} \text{ at baseline}]$) with fixed effect for treatment. Ln-transformed baseline $AUC_{(0-8)}$ value will be used as a covariate. The results from the ANOVA will be back-transformed to the linear scale to provide point estimates for each treatment as well as point estimates and 90% CI for the ratios versus placebo. The analyses of

other PD parameters (ie, C_{max} and C_{min} for total testosterone, free testosterone, and FSH) will be conducted using same ANOVA model described above.

The evaluation of LH pulse interval and amplitude (Johnson 2008) will be performed by AstraZeneca or designee.

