12.3 Determination of sample size

The sample size for this study was selected to be consistent with the research hypothesis as described in Section 1.2.

The proposed sample size is 12 evaluable patients per dose cohort with a total of 56 patients for the entire study (2 dropouts per group assumed). This study provides 76 % power versus placebo to detect a 30% change from baseline in LH at Day 7 and testosterone for the cohort at Day 28 (see Table 6).

Table 6 Sample size power

Assumed LH and testosterone change from baseline at Day 28	Evaluable subjects required		
	70% power	80% power	90% power
30% change	11	14	18
40% change	7	8	11

The number of patients that will agree to participate in the genetic research is unknown. It is therefore not possible to establish whether sufficient data will be collected to allow a formal statistical evaluation or whether only descriptive statistics will be generated. A statistical analysis plan will be prepared where appropriate.

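### The fast around the morning dose is not extended to the Day -1 hormone profile, so food intake at the baseline of every LH, FSH and testosterone ratio is uncontrolled

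*Protocol*

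**What the plan says.** Three places in the protocol set the fast, and they agree. Section 5.1 has: "Patients are to fast from 2 hours prior to the morning dose until 1 hour after dosing on Days 7 and 28". Section 5.5.2 has: "Patients will be required to fast from 2 hours prior to the morning dose until 1 hour postdose on Days 7 and 28". The Table 1 row, labelled "Fast for 2 hours prior to and 1 hour following morning dose", is marked at Visit 4 (Day 7) and Visit 7 (Day 28) and is empty at Visit 3 (Day -1).

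Other conditions are matched on Day -1. Section 3.1 says: "On Day -1, sampling will begin just prior to the anticipated time of dosing on subsequent study days and continue for 8 hours". It also asks for intensive sampling to begin by 9 AM and to start within 1 hour of the same time at later visits. The Table 1 footnotes place the first Day -1 sample at a time approximately matched to the predose window. Food is not mentioned.

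The Day -1 profile is then used throughout the pharmacodynamic analysis. In Section 11.4 the baseline value "is the time matched measurement at baseline for LH, FSH and free and total testosterone". Section 12.2.6 fits a "model on the ln-transformed ratio to baseline values", with ln baseline AUC(0-8) as a covariate, and reports "point estimates for each treatment as well as point estimates and 90% CI for the ratios versus placebo".

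**The concern.** A ratio to baseline is easiest to interpret when numerator and denominator are measured under the same conditions. The protocol takes care over clock time and the predose window on Day -1, but the one food condition it sets for the follow-up profiles is absent at baseline.

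Two things could suffer. First, if a meal changes these hormones, any average difference in eating between Day -1 and the later profiles enters each arm's ratio to baseline and the absolute, percent and ln-ratio changes. This matters most for the secondary objective in Section 2.2, which is worded as change from baseline in free and total testosterone with no reference to placebo. Second, if some patients eat before the Day -1 profile and others do not, that variation goes into every ratio and into the covariate. With about 12 evaluable patients per arm, avoidable noise is worth removing.

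**Working it through.** **1. Text check.** The fast is set for Days 7 and 28 in Section 5.1, Section 5.5.2 and Table 1. No section sets it, or any other meal condition, for Day -1. The omission is confirmed.

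**2. How much of the profile is affected.** The fast runs from 2 hours before to 1 hour after dosing, and AUC(0-8) covers 8 hours. On Days 7 and 28 food is therefore also unrestricted for 8 - 1 = 7 of the 8 sampled hours. The possible mismatch is a meal in a 3-hour window, of which only 1 hour is sampled, plus any carry-over.

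**3. The plan's own power figure.** Section 12.3 says: "This study provides 76 % power versus placebo to detect a 30% change from baseline in LH at Day 7". It states no SD and no alpha, so both had to be assumed. A two-sample t-test on the linear scale with differences 0.30 and 0.40, SD 0.30 and two-sided alpha 0.10 (matching the 90% CI) gives all of Table 6, 11/14/18 and 7/8/11, with 76.7% power at n = 12. SD 0.265 with two-sided alpha 0.05 also gives the whole table, with 75.5%. The stated 76% is consistent with either.

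**4. Bias.** Let a Day -1 meal change ln AUC(0-8) by a mean of m, the same in every arm.
- Ratio to baseline within an arm: true ratio × exp(-m).
- Ratio versus placebo: [true ratio (active) × exp(-m)] / [true ratio (placebo) × exp(-m)], so m cancels.

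For m = -0.1 or -0.2 (baseline lowered by the meal) and a true ratio of 0.70, the within-arm ratio reads 0.70 × 1.105 = 0.77 or 0.70 × 1.221 = 0.86. With no drug effect it reads 1.11 or 1.22 instead of 1.00. The opposite sign moves it the other way. The documents give neither the sign nor the size.

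A simulation of the planned model (4 arms of 12, ln baseline as covariate, 90% CI, assumed between-patient SD 0.50 and within-patient SD 0.27) agrees. The ratio versus placebo stayed at 0.70, type I error stayed near 10%, and power was 75% to 77% under a common shift.

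**5. Noise.** If a proportion p of patients eat and a meal multiplies AUC(0-8) by 1 + x, the added ln-ratio variance is p(1-p) × [ln(1+x)]². Take p = 0.5, an assumed ln-scale SD of 0.36 (variance 0.130), a difference of -ln(0.70) = 0.357, n = 12 per arm and two-sided alpha 0.10:

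| x | Added variance | Share of 0.130 | New SD | Power | Loss (points) |
|---|---|---|---|---|---|
| 0 | 0 | – | 0.360 | 76.0% | – |
| 5% | 0.25 × 0.0488² = 0.0006 | 0.5% | 0.361 | 75.8% | 0.2 |
| 10% | 0.25 × 0.0953² = 0.0023 | 1.8% | 0.363 | 75.4% | 0.6 |
| 20% | 0.25 × 0.1823² = 0.0083 | 6.4% | 0.371 | 73.7% | 2.3 |

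The SD of 0.36 is not in the protocol. It was chosen because it gives 76% on the ln scale at n = 12, but it does not return Table 6 exactly (11/14/19 and 6/7/10).

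The planned covariate absorbs part of the baseline noise. With an assumed between-patient SD of 0.50, the losses become about 0.1, 0.4 and 1.5 points.

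**6. Is 20% plausible?** If concentrations were roughly flat and the meal effect lasted only the one fasted hour, a 5% to 20% shift in AUC(0-8) would need a change of 8 × 5% = 40% to 8 × 20% = 160% in that hour. If it lasted 3 sampled hours, the change would be 40%/3 = 13% to 160%/3 = 53%. The upper end of the range is generous.

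**The case against.** The strongest defence is that the fast is a pharmacokinetic condition. Section 1.1.2 reports a 75% rise in tablet Cmax with a high-fat meal, and Day -1 has neither a dose nor a drug-concentration sample. The three passages agree with each other, so there is no contradiction in the protocol. Nothing in it says that a meal alters LH, FSH or testosterone in an undosed patient. Food is also free for most of the sampled period on every profile day. All of this stands, and it is why the point is minor. It does not remove the point: whatever its purpose, the fast fixes feeding at the start of the Day 7 and Day 28 hormone profiles and leaves it open at their reference.

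Section 3.2 might be cited in reply, since it expects no important fed/fasted difference in testosterone change. That modelling concerns differences in drug exposure. It does not cover a meal at an undosed baseline, or LH.

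Two stronger readings are tempting. A reader might infer that patients are fed on Day -1 and fasted later. The protocol does not say so: intake on Day -1 is unspecified, some patients may fast anyway, and the Laboratory Manual, which is to hold further sampling details, is not available here. A reader might also infer that the primary comparison is biased. It is not: the Day -1 profile precedes the first dose, the schedule is the same in all arms including placebo, and a common shift cancels.

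**Conclusion.** The omission is real, and its consequence is small. Feeding conditions may differ between the baseline and follow-up profiles in the 2 hours before sampling and in its first hour. The placebo comparison remains valid. Per-treatment ratios and absolute, percent and ln-ratio changes from baseline may carry a shift of unknown sign and size, although the placebo arm carries the same shift and lets a reader see it. The loss of power is about 0.2 to 2.3 points on the assumed 5% to 20% meal effect in half the patients and an assumed SD of 0.36, and about 0.1 to 1.5 points once the covariate is allowed for.

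Larger losses need a meal effect that varies widely between patients. Power in the simulation fell from 75.5% to 66% only when that effect was given a mean of 0.2 and an SD of 0.3 ln units, which nothing in the documents supports. This is a cheap improvement of minor severity.

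**What to change.** Apply the same fasting window on Day -1, from 2 hours before to 1 hour after the anticipated dosing time. Three places must change together: Section 5.1, Section 5.5.2, which repeats the rule, and the Day -1 cell of the Table 1 fasting row. Amending only some of them would create a contradiction that the protocol does not now contain.

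The cost is one short extra fast at a visit patients already attend for the 8-hour profile. Sample size, stated power and the analysis model are unchanged. The change has to be in place before a patient's Day -1 visit, because the baseline profile cannot be retaken once dosing has begun.
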